### 6.2.3 PK Population

Pharmacokinetic (PK) population will consist of all subjects who completed at least one treatment period without any protocol violations, who have evaluable plasma concentration data for Lasmiditan and/or Sumatriptan (Imitrex), and for whom at least a subset of the designated PK parameters can be determined.

The reason for excluding a subject from the PK population will be documented.

The PK population will be used for all PK analyses.

# 6.3 Coding Dictionaries Used

Adverse event and medical history verbatim terms provided by the investigator will be coded using the Medical Dictionary for Drug Regulatory Affairs (MedDRA, version 20.0). The resultant primary system organ class and preferred term will be used for AE summaries and medical history listing.

Prior and concomitant medication generic terms provided by the investigator will be coded per WHO Drug Insight and classified by preferred terms and ATC classes. The resultant ATC class and preferred term will be used for prior and concomitant medication listings.

## 6.4 Analysis Methods

#### 6.4.1 Study Subjects Disposition

Subject disposition will be tabulated by an overall summary of the number of subjects who were randomized into the study, completed all treatment periods, were included into the safety, PK population and PD population, completed the study and prematurely discontinued (with breakdown by reason for early discontinuation). The summary will be based on all enrolled subjects.

A listing will be presented to describe whether the subject completed the study, date of completion or early withdrawal, and the reason for early discontinuation, if applicable. A listing will also be provided to describe when informed consent was obtained and if the subject meets all inclusion/exclusion criteria. The date of consent and reason for entry criteria violation, if any, will be presented.

#### 6.4.2 Demographic and Baseline Characteristics

Demographic and baseline characteristics such as age, sex, race, ethnicity, height (cm), weight (kg) and BMI (kg/m²) will be summarized overall and by sequence. The summary will be based on the safety populations.

Descriptive statistics will be presented for age, height, weight and BMI. Frequency counts and percentage will be presented for sex, race and ethnicity.

The demographic and baseline characteristic data will also be presented as a data listing.

#### 6.4.3 Medical History/ Surgical History/Hospitalization

Medical history details as collected on the eCRF such as category, description, the date of onset and stop date will be presented in a by-subject data listing. History of surgery/hospitalization might be included in the medical history or presented as a separate listing.

#### 6.4.4 Prior and Concomitant Medications

All information on concomitant therapy (including all prescription/non-prescription medications, herbal medications and vitamin supplements) taken within 30 days prior to the informed consent and during the study must be recorded on the subject's eCRF and should include the name of the procedure or drug and duration of the treatment (start and stop dates). Concomitant treatments (non-pharmacological treatments) include any surgical or diagnostic procedures. Non-pharmacological treatments would not be listed.

Prior medications are defined as those taken only before the date of the first dose of the study medication i.e. stopped before the start of the study medication. Concomitant medications are defined as any non-study medication taken during the course of the study i.e. on or after the date of the first dose of the study medication. Additionally, the medications will be considered concomitant if the start and stop date of the medication are missing (not available).

Prior and concomitant medication information will be presented in a by-subject listing with anatomical-therapeutic-chemical (ATC) classification and WHO Drug Dictionary preferred term, start and stop date, dosage, route, frequency and indication.

#### 6.4.5 Protocol Deviations

The study site will record all deviations occurred through the study and all protocol deviations will be listed by subject.

### 6.4.6 Study Drug Administration

The study medication administration details including the dosing date and time, dose, fasting status will be presented in a by-subject listing.

The number and percentage of subjects receiving each of the 3 scheduled treatments will be presented by treatment group.

#### 6.4.7 Pharmacodynamic Analysis

Pharmacodynamic analysis will involve the analysis of all adverse events (AE) and the analysis of vital signs. All AEs and vital signs data will be listed and summarized.

#### **Adverse Events**

Adverse Events will be coded using the Medical Dictionary of Regulatory Activities (MedDRA version 20.0) AE coding system for purpose of summarization.

An AE will be defined as treatment-emergent (TEAE) if its time of onset or worsening is on or after the time of the study drug administration.

An AE will be defined as treatment related if its relationship to the study drug is recorded as Possibly Related or Related on the eCRF.

An overall summary of number of events and number and percentage of subjects with at least one AE, TEAE, serious TEAE, treatment-related TEAE, serious treatment-related TEAE and TEAE leading to discontinuation will be presented.

A summary of the frequency (number and percentage of subjects with events) of TEAEs will be presented by system organ class, preferred term, and treatment group. Adverse events will also be analyzed by their severity (mild, moderate, severe, life threatening or fatal) and relationship to study drug (related or not related).

A subject experiencing the same AE multiple times will be counted only once for that preferred term. Similarly, if a subject experiences multiple AEs (preferred terms) within the same system organ class then that subject will be counted only once for that system organ class. When summarizing by severity and relationship, only event with highest severity or relationship will be counted. All AEs will be presented in alphabetical order of system organ classes and preferred terms.

All information pertaining to adverse events noted during the study will be listed by subject, detailing verbatim term given by the investigator, preferred term, system organ class, start date, stop date, severity, outcome, action taken and drug relatedness. Separate listings will be created for Serious TEAEs and TEAEs leading to study drug discontinuation if deemed necessary.

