#### **Statistical Methods:**

#### PD parameters:

The number and percentage of subjects who experience adverse events and/or vital signs that are outside the normal range and clinically significant will be presented by treatment at the time of finding. AEs will be presented by severity, relationship to study drug, System Organ Class, preferred term, and treatment at the time of event. Clinically significant ECG findings will be tabulated and summarized along with the treatment. For continuous variables, data will be summarized using descriptive statistics (sample size, mean, median, and standard deviation, minimum, maximum). For discrete variables, data will be summarized using frequencies and percentages or median and range, as applicable. Data listings will be tabulated by subject.

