#### 7.14 Adverse Events and Serious Adverse Events

#### 7.14.1 Adverse Events

An AE is defined as any unfavorable and unintended sign (including abnormal laboratory findings), symptom, or disease temporally associated with the use of a study treatment or procedure that may or may not be considered related to the study treatment or procedure. AEs are collected from the time the subject signs the informed consent form until the completion of EoS. AEs that occur prior to dosing in period 1 will be recorded as medical history. Those occurring during and/or after dosing in period 1 will be recorded as adverse events.

Adverse events will be classified according to the Common Terminology Criteria for Adverse Events (CTCAE), v4.03 published June 14, 2010, the most recent version available.

The occurrence of AEs should be sought by non-directive questioning of the subject at each visit in the study. AEs may include, but are not limited to:

- Subjective or objective symptoms spontaneously offered by the subject and/or observed by the Investigator, designee, or medical staff, and
- Changes in laboratory values that are clinically relevant as assessed by the Investigator or designee and for which a medical intervention was initiated.

All AEs must be recorded in the site's study records and the AE CRF with the following information:

- 1. Relationship to Study Drug: The Investigator or designee must assess whether they consider an AE drug-related. In assessing this relationship, the Investigator or designee must use information about the drug as outlined in the Investigators' Brochure, the subject's pre-existent medical conditions/concurrent medication, and chronology of the event relative to drug administration. The following definitions will be used:
  - Reasonably or possibly related applies to those AEs that, after careful
    medical consideration at the time they are evaluated, are considered by the
    Investigator (or designee) to have at least a possible relationship to study drug.
  - Not reasonably or not possibly related applies to those AEs that, after careful medical consideration at the time of evaluation, are considered by the Investigator (or designee) to have no relationship, or no reasonable possibility of a relationship, to study drug.

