# 7.14.2 Treatment Emergent Adverse Events (TEAE)

A TEAE will be an AE that occurred during the study after a subject ingested the dose of study drug until 48 hours post-dose or that was present prior to dosing and exacerbated after the dose of study drug. This pertains to all dosing periods.

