#### **Baseline**

Baseline is defined as the latest assessment prior to the first study drug administration within each period unless otherwise specified. If the assessment occurs on the same date as the dose administration, then the time of assessment should be compared to the time of dose administration. If time is not available, protocol schedule of events should be considered.

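### The SAP's definition of treatment-emergent adverse events drops the protocol's 48-hour limit for new events and does not say which period's dose counts

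*SAP*

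**What the plan says.** Protocol 7.14.2 defines a TEAE in two limbs. The first is new onset: "an AE that occurred during the study after a subject ingested the dose of study drug until 48 hours post-dose". The second is worsening: an event "that was present prior to dosing and exacerbated after the dose of study drug", with no hour limit. The section then adds: "This pertains to all dosing periods".

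SAP 6.4.7, under Adverse Events, treats onset and worsening alike. An AE is treatment-emergent "if its time of onset or worsening is on or after the time of the study drug administration". The resulting flag feeds the overall AE summary and the TEAE tables by system organ class, preferred term and treatment group. Nothing else in the SAP restores a 48-hour limit or ties the flag to a period. The SAP does tie other definitions to the period: "Baseline is defined as the latest assessment prior to the first study drug administration within each period unless otherwise specified".

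Three other protocol statements bear on this:

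- On collection, 7.14.1 says "AEs are collected from the time the subject signs the informed consent form until the completion of EoS" and "AEs that occur prior to dosing in period 1 will be recorded as medical history".
- On attribution, the synopsis (Statistical Methods, PD parameters) says "AEs will be presented by severity, relationship to study drug, System Organ Class, preferred term, and treatment at the time of event".
- On use, 8.4.1 makes TEAEs the discrete pharmacodynamic outcome and plans a model comparing their frequency between treatments.

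**The concern.** The two documents state different rules for the same variable, and the SAP does not say that it has changed the protocol's rule. In a three-period cross-over, *the study drug administration* can mean any earlier dose or the dose of the current period, and the SAP does not choose.

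The variable matters. AEs are part of the primary endpoint, and SAP 4.1 keeps them as one of two pharmacodynamic endpoints. Collection runs to the end-of-study visit (EoS), so any AE that starts more than 48 hours after a dose will be in the database. It would be a TEAE under the SAP and not under the protocol. The TEAE tables would then pool events up to about a week after a single dose with those in the two days after it.

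The longer window also makes attribution matter more. Neither document says which treatment receives an event that starts in the wash-out or at check-in for the next period, so two programmers could produce different tables by treatment.

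**Working it through.** The plan gives no figure for this point, so there is nothing to reproduce. The check compares, for a subject who takes all three doses, the hours in which a new AE counts as a TEAE.

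**Inputs**

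- Doses on Study Days 1, 8 and 15 (study-day grid, Protocol 3.1).
- EoS on Day 21 ± 2 days (Protocol 3.3.4 and 3.3.5).
- New-onset limit of 48 h per dose (Protocol 7.14.2).
- Assumption: the same clock time for each dose and for EoS.

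**Protocol window:** 3 × 48 = 144 h.

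**SAP, read as any time after the first dose:** (EoS day − 1) × 24.

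| EoS day | SAP window | Ratio to 144 h | Extra time |
|---|---|---|---|
| 19 | 18 × 24 = 432 h | 3.00 | 288 h (12 days) |
| 21 | 20 × 24 = 480 h | 3.33 | 336 h (14 days) |
| 23 | 22 × 24 = 528 h | 3.67 | 384 h (16 days) |

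At Day 21, 336/480 = 70% of the post-dose time counts under the SAP only. On this reading the SAP's AE and TEAE rows coincide, because events before the Period 1 dose go to medical history.

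**SAP, read as that period's dose, with each period starting at check-in:** pre-dose time in Periods 2 and 3 drops out, so the window is 480 − 2 × (hours from check-in to dose). The check-in time is not stated.

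- 24 h before dosing: 480 − 48 = 432 h, ratio 3.00.
- 12 h before: 480 − 24 = 456 h, ratio 3.17.
- 36 h before: 480 − 72 = 408 h, ratio 2.83. This bound is probably too wide. Protocol 3.3.3.2 puts the 16-hour sample on Day 1, so dosing is by about 08:00 and a Day −1 check-in is at most about 32 h earlier, giving 480 − 64 = 416 h.

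On this reading the AE and TEAE rows can differ only by pre-dose events in Periods 2 and 3.

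**If the six-day wash-out meant six days from dose to dose**, taking 144 h for each window: 3 × 144 = 432 h, ratio 3.0.

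**Weight of one subject:** 100/42 = 2.4 percentage points, or 100/36 = 2.8.

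**Illustration only.** The documents give no rate of late-onset events. Assume a constant rate *r* per subject-day and assign each event to the last dose taken. The extra time beyond 48 h is 5 days in Periods 1 and 2 and 4 days in Period 3. The chance of at least one event in *d* extra days is 1 − exp(−*rd*), averaged over periods as (2 × 5-day value + 4-day value)/3:

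| *r* per day | Mean chance | × 42 subjects |
|---|---|---|
| 0.005 | 0.0231 | 1.0 |
| 0.01 | 0.0456 | 1.9 |
| 0.02 | 0.0891 | 3.7 |
| 0.03 | 0.1306 | 5.5 |

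These are upper limits on the average number added per treatment, because some of these subjects would already have had an event within 48 h.

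**The case against.** The strongest reply is that the consequence is small. All three treatments share one definition and the sequences are balanced, so no treatment is favoured. SAP 6.4.7 reports only counts and percentages, with no test. It covers all AEs as well as TEAEs, and the wider window loses no event. AE start dates and dosing times are listed, so late onsets can largely be found by hand. Protocol section 8 also leaves deviations from planned analyses to be justified in the study report. All of this stands. It limits the seriousness, but it does not remove the conflict.

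The second reply is that the per-period ratio depends on where a period ends. Protocol 3.1 and SAP 2.2 describe each dosing period as Days −1, 1 and 2, with the wash-out separate. If TEAEs were confined to those days, the window would end less than 48 h after the dose. That is fair, and the threefold ratio does not hold on that reading. However, the SAP does not state that reading, and it would not match the protocol either.

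Third, the SAP's listings by period and treatment, and the synopsis rule on treatment at the time of an event, point towards a per-period reading. They do, but they leave wash-out events unassigned.

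Finally, the assumed event rates have no source in the documents and should carry no weight. The protocol's own definition is not a clean 48-hour window, because its worsening limb is open-ended.

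**Conclusion.** The concern holds. This is a conflict between two stated rules, not a missing detail: the protocol limits new-onset TEAEs to 48 hours in every period, and the SAP sets no limit and names no period's dose.

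Read as any time after the first dose, the SAP window is about 480 h (432 to 528 h) against 144 h. This rests on the Day 1, 8 and 15 grid and a subject who takes all three doses. Read by period with a 24-hour check-in, it is about 432 h. The 48-hour limit is absent either way.

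Counts differ only if new AEs start more than 48 h after a dose. The documents do not say how often that happens, so the effect on the tables is unknown and may be small. No bias between treatments is claimed. The point should still be corrected, because the flag defines a main outcome.

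**What to change.** In SAP 6.4.7, adopt the protocol definition: new onset from dosing to 48 hours after it within each period, attributed to that period's treatment, with the worsening limb as Protocol 7.14.2 words it. Use that flag for the TEAE tables and for any treatment comparison. State how AEs after 48 hours are attributed (for example, to the last treatment received) and where they are reported; a separate table is optional.

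If the wider window is intended, say so in the SAP, justify the departure from Protocol 7.14.2, give the attribution rule, and show the 48-hour count alongside.

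The cost is a few sentences, one derived flag and perhaps one extra table. No new data are needed: Protocol 7.14.1 already requires AE start and end dates and times, and SAP 6.4.6 lists dosing dates and times.

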## 8. STATISTICAL METHODS

Before database lock, a statistical analysis plan (SAP) will be issued as a separate document, providing detailed methods for the analyses outlined below.

Any deviations from the planned analyses will be described and justified in the final integrated clinical study report.

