## 8.2.3 Analysis Populations

Pharmacodynamic population: All randomized subjects who received at least one dose

of any study drug.

Safety population:

All randomized subjects who received at least one dose

of any study drug.

Pharmacokinetic population:

All subjects with evaluable PK data will be included in the pharmacokinetic population. Subjects with incomplete PK data, e.g. data missing from one entire study period, will be listed and the derived PK parameters will not be

considered for summary statistics and analytical

evaluations.

The primary results will be based on the pharmacodynamic population. All safety analyses will be based on the safety population.

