## 8.4 Pharmacodynamic Analyses

#### 8.4.1 Adverse Events

The discrete outcome variables are the treatment emergent adverse events. A general linear random model will be used to compare and contrast the frequency difference of TEAEs in the different treatment groups, lasmiditan 200 mg co-administered with sumatriptan (Imitrex) 100 mg, lasmiditan 200 mg co-administered with lasmiditan placebo 200 mg, or sumatriptan (Imitrex) 100 mg co-administered with lasmiditan placebo 200 mg.

Adverse events will be summarized by treatment group (Medical dictionary for medical activities (MedDRA) terminology (latest version), severity and relation to study drug. The descriptive statistics presented for each system-organ class and preferred term will be the number of subjects with event (N), the percent of subjects exposed with event (%), and the number of events (E). All AEs will be listed by subject, including demographic information, dose sequence, MedDRA latest version, system organ class, and preferred term.

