#### 3. DATA ANALYSIS CONSIDERATIONS

# 3.1 Determination of Sample Size

The sample size calculation for this study is based on the proportion of adverse events in the two treatment groups namely the combination therapy (Lasmiditan + Sumatriptan) vs a single drug (Lasmiditan). The calculation is performed using a test for two proportions in a repeated measures design. To ensure that at least 36 subjects complete, 42 subjects (approximately 60% female) will be enrolled.

The sample size of 36 subjects will provide at least 80% power to show equivalence of the PK of Lasmiditan in the absence and presence of Sumatriptan (Imitrex), assuming a 25% within subject coefficient of variance.

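### SAP 6.4.7 leaves out, without giving a reason, the between-treatment TEAE comparison that Protocol 8.4.1 plans and that SAP 3.1 names as the basis of the sample size

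*SAP*

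**What the plan says.** - **Objective.** Protocol 2.1 and SAP 2.1 set the primary objective as a PD comparison of the combination (treatment C) with lasmiditan alone (A) and with sumatriptan alone (B).
- **Protocol analysis.** Section 8.4.1: "A general linear random model will be used to compare and contrast the frequency difference of TEAEs in the different treatment groups". Section 8 gives the SAP its task: "a statistical analysis plan (SAP) will be issued as a separate document, providing detailed methods for the analyses outlined below".
- **SAP sizing.** Section 3.1 bases the calculation on the proportion of adverse events, combination versus lasmiditan, and adds: "The calculation is performed using a test for two proportions in a repeated measures design". It also states at least 80% power for PK equivalence with 36 subjects at a 25% within-subject CV.
- **SAP analysis.** Section 6.4.7 opens with "All AEs and vital signs data will be listed and summarized". Under Adverse Events it adds "A summary of the frequency (number and percentage of subjects with events) of TEAEs will be presented by system organ class, preferred term" and breakdowns by severity and relationship.
- **TEAE definition.** Protocol 7.14.2: "an AE that occurred during the study after a subject ingested the dose of study drug until 48 hours post-dose", plus events present before dosing that worsen afterwards. The SAP counts an event "if its time of onset or worsening is on or after the time of the study drug administration", with no end time.

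**The concern.** If the SAP is followed as written, the only between-treatment model that the protocol plans for a PD endpoint is never fitted, and the comparison cited for the sizing is never made. Readers would get three columns of percentages for AEs. In a crossover, the precision of a difference depends on how many subjects have an event on one treatment and not on the other, and those columns do not show that. A comparison added after unblinding would leave the outcome, contrast and method open to choice. The differing TEAE windows mean that even the descriptive counts could change with the document followed.

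**Working it through.** **1. The plan's own figures.** Enrolling 42 to retain 36 allows for 6/42 = 14.3% loss, which is consistent. The AE-based calculation cannot be reproduced, because neither document gives the AE rates, within-subject correlation, alpha or power.

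The PK statement can be checked. The log-scale SD is √ln(1 + 0.25²) = 0.246, and the standard error of a paired difference is 0.246 × √(2/36) = 0.058. Two one-sided 5% tests against 80–125%, with 35 degrees of freedom, give power of 96.6% at a true ratio of 1.00 and 89.5% at 0.95. The true ratio is not stated, so both values are assumed. The claim of at least 80% holds for either.

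**2. Side by side.**

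| Place | TEAE comparison between treatments |
|---|---|
| Protocol synopsis, PD parameters | Descriptive only, by treatment at the time of the event |
| Protocol 8.4.1 | Model across the three treatments |
| SAP 3.1 | Repeated-measures comparison of two proportions, C versus A |
| SAP 6.4.7 | None, and no reason given |

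The only treatment contrasts with intervals in the SAP are the PK ratios in 6.4.9.2.

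**3. What the percentages hide.** Assume that 36 subjects have both periods, with any TEAE in 18/36 (50%) on A and 27/36 (75%) on C. The difference is 9/36 = +25 points however the pairs fall. Two arrangements with these same totals:

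| Event on C only | Event on A only | Difference | 95% score CI (Tango), points | Exact McNemar p |
|---|---|---|---|---|
| 9 | 0 | +25 | 12.9 to 41.1 | 0.004 |
| 14 | 5 | +25 | 1.3 to 45.8 | 0.064 |

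The SAP's table would be identical in both cases.

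**4. Why the sizing inputs matter.** At the same assumed rates, the planning half-width is 1.96 × √[(p₁₀ + p₀₁ − 0.25²)/36], where p₁₀ and p₀₁ are the probabilities of an event on A only and on C only.

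| Within-subject correlation | Expected discordant pairs | 95% half-width, points | Exact McNemar power, two-sided 5% |
|---|---|---|---|
| 0 | 18.0 | 21.6 | 50% |
| 0.3 | 13.3 | 18.1 | 65% |
| 0.5 | 10.2 | 15.4 | 82% |

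The only 200 mg TEAE rate in the protocol is 86% (Section 1.2, Phase 2 migraine patients). If it applied here, a rise to 100% would make every discordant pair fall the same way. Exact McNemar then needs at least 6 discordant pairs (2 × 0.5⁶ = 0.031, whereas 2 × 0.5⁵ = 0.0625), and P(Bin(36, 0.14) ≥ 6) = 39%. So whether 36 suits an AE comparison depends entirely on inputs that are not stated.

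**5. The window.** The schedule in Protocol 3.1 places doses on study Days 1, 8 and 15, which is 7 × 24 = 168 h apart. In Periods 1 and 2 an open window can therefore run to 168/48 = 3.5 times the protocol's. After the Day 15 dose, follow-up to the end-of-study visit on Day 21 ± 2 is 4 to 8 days (96 to 192 h), or 2 to 4 times. If unrelated later events struck an assumed share b of subjects independently in each period, a 25-point difference would shrink to 25 × (1 − b): 23.8, 22.5 or 20.0 points for b = 5%, 10% or 20%.

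**The case against.** The strongest reply is that this is a Phase 1 study with no PD hypothesis, margin or success rule. The protocol synopsis is purely descriptive for PD, and Protocol 8 allows deviations to be justified in the final report. The by-subject listings preserve the pairs, so no data are lost. All of this is true, and it lowers the severity. It does not remove the omission: the protocol body plans the model, the SAP is meant to detail it, and SAP 3.1 itself relies on an AE comparison.

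Four stronger readings are tempting and are not supported.

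- **The sample size has no basis.** The same 36 carries a PK power statement that checks out. Only the AE rationale cannot be verified.
- **The SAP dropped a promised confidence interval.** Protocol 8.4.1 promises a comparison, not an interval. The PK interval follows from the protocol's own PK section, which labels the paired t-test its primary statistical analysis. Reporting intervals for TEAEs is a recommendation of this review.
- **The protocol declares the PD results to be the primary results.** Section 8.2.3 says "The primary results will be based on the pharmacodynamic population", which names an analysis set. The primary objective is support enough.
- **AEs are the only PD item that differs between the documents.** The synopsis plans counts of clinically significant out-of-range vital signs that SAP 6.4.7 lacks, and SAP 4.1 moves ECG, part of the protocol's primary endpoint, to safety. This point neither covers nor clears those differences.

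On the window, the synopsis assigns AEs by treatment at the time of the event, and the SAP lists data by period and treatment. That partly answers the question of allocation. It does not reconcile 48 hours with an open end, and the SAP states no allocation rule for the TEAE counts.

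**Conclusion.** The point holds on the text alone: a planned TEAE comparison, also cited for the sizing, is missing from the SAP without explanation, and the TEAE window is inconsistent. It should be fixed before database lock, but it does not invalidate the trial.

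The illustration in step 3 shows the size of the gap: one and the same table is compatible with a lower confidence limit of 12.9 points or of 1.3 points. That rests on assumed counts and 36 complete pairs. The power, half-width and dilution figures also rest on assumed rates, correlations and background event shares, since the documents give none for healthy subjects.

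**What to change.** **SAP 6.4.7.**
- Reconcile the TEAE window with Protocol 7.14.2, and state that each event is assigned to the period of the most recent dose.
- Add one prespecified within-subject comparison of the proportion of subjects with at least one TEAE: a binary mixed model with treatment and period as fixed effects and subject as a random effect. Use the whole PD population, including subjects with incomplete periods.
- Report C−A and C−B risk differences with 95% CIs, with equal standing, because the objective names both single drugs.
- Only if the model does not converge, use a paired score CI with exact McNemar in subjects who have both periods of the contrast.
- If the protocol's model is deliberately omitted, say so and give the reason.

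**SAP 3.1.** State the AE rates, within-subject correlation, alpha and power behind the AE sizing. Otherwise, state that they are unavailable, that 36 rests on the PK power, and that the AE comparison is for estimation.

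**Cost.** A little SAP text and programming; visits and data collection are unchanged. The sponsor may have to acknowledge that the AE comparison has no documented power.
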